2.5. Definition of Study Dates and Observation Period End Dates

The study dates and period end dates will be used to define the time period for data included in the analysis of efficacy and safety endpoints for the different observation periods (defined in Section 2.6).

Study Day 1 date: the date of randomization of the subject.

End-of-Study (EOS): the date of the last study-related procedure for the subject (EOS is defined as last assessment day during the study, including the Day 210/Post-Treatment Follow Up visit) and is defined as the minimum (last assessment day during the study, death date).

Double-Blind period start date will be the date of randomization.

Double-Blind period end date will be defined as the completion/early withdrawal date (date of completion or early withdrawal [any reason including death] from the double-blind period).

Up-to-Day 180 observation period end date will be defined as follows;

- Day 180/EODB completion date (for subjects who completed the double-blind period) or
- Death date (subjects who died during the double-blind period [DB reason=death] or during any time from randomization through Day 180 [died post withdrawal from DB but before Day 180/EODB visit] or
- Maximum (double-blind withdrawal date, randomization date + 180 days) for subjects who withdrew early from the double-blind period [any reason other than death] and had not died during the time from randomization through Day 180

First dose date: the date on which the first dose of study drug is taken by the subject. If missing or partial for a subject who takes study drug, the first dose date is set to the randomization date.

Last dose date: the date on which the last dose of study drug is taken by the subject (dose end date). If the dose end date is missing or partial for a subject who takes study drug, the last dose date is set as follows

- Maximum (Minimum (discontinuation date in the double-blind period [including death date during double-blind period], last visit date when drug is dispensed + number of pills dispensed - number of pills returned at following visit), imputed partial last dose date, exposure start date of last record))
 - Imputation rule for partial dates: If only the day is missing, then day imputed to the last day of that month. If day and month are missing, the date will be imputed to the start date if year is the same, else imputed to January 1st.

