2.6.1. Up-to-Day-180 Observation Period

This observation period includes data from randomization to Up-to-Day 180 end date (defined in Section 2.5).

Event: All efficacy events (with respect to deaths, *VTE-related deaths are counted as events for primary efficacy endpoint. For the secondary efficacy endpoints, all-cause deaths are counted as events*) that occurred from randomization through the Up-to-Day 180 end date (Section 2.5) will be included in the analysis of this observation period.

- Event time - The time to event is defined as the time from randomization to the time of the first event during this observation period.

Censoring: Subjects who did not experience an event during this observation period will be censored at the last day of their complete assessment for study outcomes.

Subjects who died during this observation period will be censored as of their death date for endpoint analyses not related to death.

- Censoring time - The time to censoring is defined as the time from randomization to the minimum of (last day of their complete assessment for study outcomes during the double-blind period [double-blind completion/withdrawal], death date [non VTE-related deaths for primary efficacy composite endpoint]).

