 - a. If subject experiences an efficacy composite endpoint event (primary or secondary, including VTE-related deaths) after withdrawing from the study and the time to the occurrence of the event is prior to Day 180, then this event and corresponding time to the occurrence of the event will be included in the analysis of primary efficacy composite endpoint. If subject dies (all causes other than VTE-related) after withdrawing from the study and reported on Day 210 but event time is prior to Day 180, then this event and corresponding time to death will be included in the all-cause mortality endpoint analysis
 - b. If a subject does not experience any efficacy composite endpoint event (primary or secondary) in the study, then this subject will be censored. The time to censoring is defined as the time from randomization to the minimum of (last day of their complete assessment for study outcomes during the double-blind period/Day 180 [double-blind withdrawal date for those who withdrew], or death date [censored at death date for analysis not related to the specific death endpoint]).

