5.4.2. Analysis Methods

Analysis of the key secondary efficacy endpoints will follow the same approach as in the analysis of the primary efficacy composite endpoint analysis. The analysis will be based on the ‘Up-to-Day 180’ observation period for ITT population with censoring as defined above (Section 2.6). Each of the key secondary endpoints will be tested using a log-rank test, stratified by tumor type.

For each of these two key secondary endpoint analyses, a Cox proportional hazard model with treatment and stratification factor as covariates will be fitted. A point estimate along with 2-sided 95% CI for the treatment effect of RRR (RRR=100 x [1-HR] %) will be provided.

The cumulative event rate derived from Kaplan-Meier estimate will also be displayed graphically to evaluate the timing of event occurrence and the consistency of the treatment effect over time.

Summary of Key Secondary Efficacy Endpoints Analysis Methods			
Endpoint	Observation Period	Analysis Population	Method
Key Secondary Endpoints 1. Composite of symptomatic VTE events or VTE-related death 2. All-cause mortality (CEC Adjudicated Events)	Up-to-Day 180	ITT	Kaplan-Meier Estimates (Cumulative event rates and stratified log-rank test) Cox-model (HR, 95% CI)

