5.5. Adjustment for Multiplicity

Superiority of rivaroxaban over placebo on the primary efficacy composite endpoint will be first established. If this is established, then a sequential approach using a closed testing hierarchical procedure (to control the family-wise type I error rate at alpha at 5%, 2-sided) will be used to test the following two secondary hypotheses:

- symptomatic VTE events + VTE-related deaths
- all-cause mortality

Overall Hierarchy of Testing Multiple Hypothesis	
Primary Efficacy Composite Endpoint (ITT/Up-to-Day 180)	
• Time to first occurrence of symptomatic lower extremity proximal DVT, asymptomatic lower extremity proximal DVT, symptomatic lower extremity distal DVT, symptomatic upper extremity DVT, symptomatic non-fatal PE, incidental PE or VTE-related death	$\alpha=0.05$
↓	
Secondary Efficacy Endpoints (ITT/Up-to-Day 180)	
• Time to first occurrence of symptomatic VTE events and VTE-related death	$\alpha=0.05$
↓	
• All-cause mortality	$\alpha=0.05$

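### All-cause mortality up to Day 180: deaths after early withdrawal count as events, but withdrawers not known to have died are censored at withdrawal, so follow-up depends on the outcome

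*SAP*

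**What the plan says.** **Event window.** SAP 2.5 ends the Up-to-Day 180 period, for withdrawers who have not died by Day 180, at "Maximum (double-blind withdrawal date, randomization date + 180 days) for subjects who withdrew early from the double-blind period". It therefore runs to at least Day 180.

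**Events.** SAP 4.6, scenario 2a, includes efficacy events that occur "after withdrawing from the study and the time to the occurrence of the event is prior to Day 180". On all-cause mortality it says of a death "reported on Day 210 but event time is prior to Day 180, then this event and corresponding time to death will be included".

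**Censoring.** SAP 2.6.1 sets the censoring time at the minimum of "last day of their complete assessment for study outcomes during the double-blind period [double-blind completion/withdrawal], death date". Scenario 2b of 4.6 repeats this as the "double-blind withdrawal date for those who withdrew".

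**Use.** SAP 5.4.2 applies the Section 2.6 censoring to both key secondary endpoints. SAP 5.5 puts all-cause mortality last of three tests in a procedure meant "to control the family-wise type I error rate at alpha at 5%, 2-sided".

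**Data collected.** SAP 5.7 says vital status was collected at Day 210 for all randomized subjects except those who died in the double-blind period. SAP 1.2.1 and 4.6 add public records, where local rules allow, for subjects who withdrew consent or were lost to follow-up.

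**The concern.** Take two subjects who both withdraw on Day 60. One dies on Day 150 and contributes 150 days and an event. The other is alive at the Day 210 contact and contributes 60 days and no event. Time after withdrawal enters the risk set only for those who go on to die. Kaplan-Meier, log-rank and Cox methods require that leaving the risk set does not depend on the future outcome, and this rule breaks that by construction. The missing survival time is largely collected, and the SAP gives no reason for discarding it.

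Two things are at stake: the reported 180-day mortality in each arm, and the third confirmatory test if the arms differ in early withdrawal.

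**Working it through.** **Step 1, inputs.** The SAP gives no mortality level, no withdrawal rate by arm and no capture rate for later deaths, so there is no stated mortality figure to reproduce. From the SAP: about 800 subjects (1.2), so 400 per arm, and 20% dropout (1.4). That 20% may include deaths, because 2.5 defines the double-blind end as completion or "early withdrawal [any reason including death] from the double-blind period". Assumed: 180-day mortality 20% (10% and 30% as the range), exponential times, and withdrawal independent of death.

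**Step 2, Kaplan-Meier with full capture.** Let one time unit be 180 days, p the true mortality and w the non-death withdrawal. Then S(t) = (1−p)^t and G(t) = (1−w)^t. Complete follow-up has S(t) at risk. Under the SAP rule, those who will die by Day 180 stay until death, and the rest stay only until withdrawal:

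Y(t) = [S(t) − S(1)] + S(1)·G(t)

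The hazard is inflated by S(t)/Y(t). For p = w = 20%:

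- at mid-period: 0.894 / (0.894 − 0.800 + 0.800 × 0.894) = 0.894/0.810 = 1.10
- at Day 180: 0.800/0.640 = 1.25

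Integrating, the cumulative hazard rises from −ln 0.8 = 0.223 to 0.248, and the reported mortality is 1 − exp(−0.248) = **22.0%**. At w = 20%, true 10% and 30% become 11.1% and 32.6%. If the dropout figure includes deaths, the effect shrinks. With 10% mortality and 10% non-death withdrawal (1 − 0.9 × 0.9 = 19% in total), 10.0% becomes 10.5%. With 20% and 5% (1 − 0.8 × 0.95 = 24% in total), 20.0% becomes 20.4%.

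**Step 3, changed risk and incomplete capture.** Let the death hazard λ become kλ after withdrawal, and let later deaths be captured with probability c. Let ω be the withdrawal hazard, A(t) = exp(−(λ+ω)t) the share alive and not withdrawn, and B(t) = ∫₀ᵗ ω·exp(−(λ+ω)s − kλ(t−s)) ds the share alive and withdrawn. The SAP rule gives a Kaplan-Meier hazard of (λA + ckλB) / (A + cB[1 − exp(−kλ(1−t))]). With λ and ω from 20% each:

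| k | c | True | SAP rule |
|---|---|---|---|
| 0.5 | 100% | 19.1% | 21.0% |
| 2 | 100% | 21.7% | 23.6% |
| 3 | 100% | 23.2% | 24.9% |
| 3 | 50% | 23.2% | 22.5% |
| 3 | 25% | 23.2% | 21.3% |
| 2 | 25% | 21.7% | 20.9% |

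The rate is overstated with full capture and understated in the last three rows.

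**Step 4, the test when there is no true effect.** At w = 30% the step 2 cumulative hazard is 0.264, so 30% on placebo against 20% on rivaroxaban gives a hazard ratio near 0.248/0.264 = 0.94. Simulation (40,000 trials, 400 per arm, 20% mortality, full capture, unstratified log-rank, nominal 2.5% each way):

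| Withdrawal, placebo vs rivaroxaban | HR | False superiority | False harm |
|---|---|---|---|
| 25% vs 20% | 0.97 | 3.9% | 1.6% |
| 30% vs 20% | 0.94 | 5.7% | 1.0% |
| 20% vs 30% | 1.06 | 0.9% | 5.5% |

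Equal 20% withdrawal gives HR 1.00 and 5.1% two-sided. Separate repeats of the 30% vs 20% case gave false superiority of 5.4% to 5.8%. At 90% or 75% capture that case gives HR 0.947 or 0.955 and 6.5% or 5.7% two-sided.

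**Step 5, other planned analyses.** The Post-Randomization and Post-First Dose periods (2.6, 5.2.3) and the worst-case analysis (5.2.5.2) serve only the primary composite. SAP 5.6.2 analyzes the key secondary endpoints again on the same period. The Cochran-Mantel-Haenszel test in 5.7 lies outside the hierarchy.

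**Step 6, VTE.** Putting the 14.5% placebo rate into the step 3 formula with 20% withdrawal gives 16.0%, 15.3% and 14.9% at full, half and quarter capture. With doubled hazard (true 15.8%) it gives 17.3%, 15.9% and 15.2%. The error can go either way.

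**The case against.** **The wording might allow later censoring.** One could read the last complete outcome assessment, for mortality, as the Day 210 contact. The text closes that reading: the assessment must fall within the double-blind period, and both 2.6.1 and 4.6 name the withdrawal date in brackets.

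**The direction is not fixed.** A reader might infer that mortality is always overstated. Step 3 shows otherwise, and registry data depend on local rules, so capture may be incomplete. This objection stands, and the direction must be stated as conditional on capture.

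**The test is harmed only by an assumed imbalance.** A reader might infer that the rule favors rivaroxaban or inflates the error rate as such. The documents do not support that. The trial is double-blind, no withdrawal rate by arm is given, and equal withdrawal leaves the test nearly unbiased. Mortality is also tested only after two successes, and the planned test is stratified by tumor type while the simulation is not. This limits the seriousness but does not make the rule sound.

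**The VTE rule has a rationale.** A reader might infer that primary-endpoint censoring should be rewritten too. The Day 210 contact is by telephone and cannot exclude asymptomatic DVT, which scheduled ultrasound looks for. Extending VTE follow-up is not reliably less biased: with doubled hazard (true 15.8%) and status known for half or a quarter of withdrawers, it gives 15.2% or 14.9%, no better than the SAP rule in step 6. The primary endpoint also has a supportive analysis that follows subjects to last contact. No better primary rule is claimed.

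**A supportive analysis may have been intended.** The amendment history mentions a post-randomization analysis of the key secondary endpoints. The current sections contain none, so it cannot be relied on; the difference itself is not counted as an error.

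**Conclusion.** The point holds for all-cause mortality. The event rule and the censoring rule are plainly mismatched in the current text, and together they govern an alpha-controlled test. The mismatch itself is certain; its size is not.

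With near-complete capture, 20% non-death withdrawal and true mortality of 10% to 30%, the reported rate is about 1 to 2.6 percentage points too high. The error is smaller if non-death withdrawal is lower, and its sign can reverse if capture is poor and risk rises after withdrawal. The hazard ratio stays near 1.00 under the null with equal withdrawal and moves to about 0.94 or 1.06 with a 10-point imbalance. Mortality level, imbalance, capture and independence of withdrawal are all assumptions. SAP 1.5 itself says pancreatic subjects have higher VTE risk and leave early more often.

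This should be fixed, but it does not show that any conclusion of the trial would be wrong.

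**What to change.** In 2.6.1 and 4.6 (scenario 2b), for all-cause mortality only, censor subjects not known to be dead at min(last date documented alive, including the Day 210 contact; randomization + 180 days). Use a registry as a known-alive date only where it positively documents vital status at that date. Finding no death record is not enough: if that is read as alive, then at 50% capture and doubled hazard a true 21.7% is reported as about 19.9%.

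Add a sensitivity analysis that stops both deaths and follow-up at withdrawal. For the VTE endpoints, state that the same mismatch exists and add a sensitivity analysis that aligns events and follow-up. The primary censoring rule can stay.

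**Effect.** With complete vital status the change returns 20.0%, and at 20% vs 30% withdrawal HR 1.00 and 4.9% two-sided error. If all deaths are found but only 90% or 75% of surviving withdrawers have a later date, it gives 20.2% or 20.5% (HR 0.995 or 0.987).

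**Cost.** Reprogrammed censoring dates, slightly lower reported rates and the added sensitivity analyses. Some bias remains if vital status is incomplete and risk changes at withdrawal: with status known for 75% and tripled hazard, the new rule understates by 0.7 points where the SAP rule overstates by 0.6. The change should be made before unblinding.

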1.2. Study Design

[figure not shown]
This is a multicenter, randomized, double-blind, placebo-controlled, parallel-group, superiority study comparing the efficacy and safety of rivaroxaban with placebo for primary prophylaxis of VTE (defined as DVT and/or PE) in ambulatory adult men and women, 18 years of age and older, with various cancer types who are scheduled to initiate systemic cancer therapy as a component of their standard of care anticancer regimen, who have a baseline Khorana thromboembolic risk score of ≥ 2 , and are judged by the investigator or qualified designee to be an appropriate candidate for treatment with either placebo (10 mg orally once daily for 180 days) or rivaroxaban (10 mg orally once daily for 180 days) for thrombo-prophylaxis based on their clinical status.

The study consists of 3 periods: a 2-week screening period, a 180-day double-blind treatment period with an End-of-Treatment (EOT) visit [for subjects who permanently stop study drug], and a 30-day post-treatment follow-up period with a Day 210/End-of-Study (EOS) visit. The duration of participation in the study for each subject is approximately 32 weeks.

A target of approximately 700 subjects will be randomly assigned into the study in a 1:1 ratio to 1 of 2 treatment groups (rivaroxaban 10 mg qd and placebo) with approximately 350 subjects per treatment group. Towards the end of the enrollment phase, the planned total of subjects to be randomized into the study was revised to approximately 800 subjects due to a higher than originally anticipated subject discontinuation rate. In addition, subjects will be stratified at randomization by tumor type (APC or non-APC) such that approximately 25% of the subjects randomly assigned are those with APC.

Randomized subjects will continue with their recommended systemic cancer therapy (SCT) during the study period and will be examined by compression ultrasonography (CU) at every 8-week intervals. Subjects permanently discontinuing the study drug will be required to have a CU performed within 2 days of receiving their last dose of study drug.

Figure 1: Schematic Overview of the Study

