In this study with a six-month planned treatment with rivaroxaban, the primary efficacy outcome variable is a composite of any symptomatic DVT, proximal asymptomatic DVT, any PE, and VTE-related death. The study design allows fixed treatment duration of 6 months on each successfully randomized subject. Assuming a cumulative incidence rate of 14.5% for the primary composite events in the placebo group and 6.0% cumulative incidence rate in the rivaroxaban treatment group, a total sample of about 700 randomized subjects (350 per treatment group) will be required to demonstrate approximately 60% relative risk reduction (RRR) in the primary efficacy composite endpoint with a 2-sided Type 1 error rate of 5% and >90% statistical power (calculation performed by EAST 6.3 software) assuming a 20% discontinuation rate. Towards the end of the enrollment phase, approximately 800 subjects were planned to be randomized into the study due to the high subject discontinuation rate. In addition, this sample size will allow for 80% statistical power in each stratum (APC or non-APC) for slightly larger differences in incidence rates between the two randomized treatment groups to be statistically significant.

Essentially, the above overall sample size estimate is calculated based on the following assumptions:

- Effect size: absolute difference in event rates = 8.5%, RRR = 58.6%
 - Primary efficacy composite endpoint event rate in the placebo arm: 14.5%
 - Primary efficacy composite endpoint event rate in the rivaroxaban arm: 6%
- Power: >90%
- Overall α level: 5%, 2-sided
- Probability of dropping out of the study: 20%
- Duration of enrollment period: 12 months
- Duration of study: 6 months (fixed for each randomized subject)

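### Primary censoring follows the withdrawal date rather than an outcome assessment, while withdrawers' events count past that date, so the Kaplan-Meier rates can be biased in either direction

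*SAP*

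**What the plan says.** Section 2.6.1 gives the primary censoring time as the earlier of death and the "last day of their complete assessment for study outcomes during the double-blind period [double-blind completion/withdrawal". Section 4.6(1b) uses the same formula for subjects who stop drug but complete the period. Section 4.6(2b) settles the bracket for the others: "double-blind withdrawal date for those who withdrew". Section 2.5 defines the double-blind end date as the date of completion or of early withdrawal for any reason, and does not require an outcome assessment on it.

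Events follow a different clock. For withdrawers who have not died, Section 2.5 ends the Up-to-Day 180 period at the later of withdrawal and randomization + 180 days. Section 4.6(2a) puts events after withdrawal but before Day 180 into the primary analysis.

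On ascertainment, Section 1.2 says that subjects "will be examined by compression ultrasonography (CU) at every 8-week intervals" and asks for a scan within 2 days of the last dose on permanent drug discontinuation. Section 1.2.1 adds a telephone contact at Day 210 for all subjects.

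**The concern.** There are two separate faults.

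- **Unassessed time counts as event-free.** The stated principle is censoring at the last full outcome assessment, but the operative date is the recorded withdrawal. The two agree if the subject leaves at a visit with a full assessment, and differ if the subject is lost between visits. As a hypothetical case, take a subject last seen and scanned on Day 56, who misses Week 16 and is recorded as withdrawn on Day 150. That subject carries 150 − 56 = 94 days of unassessed time and sits in the risk set for the Day 112 scan without having it. This pushes rates down.
- **Event and censoring windows do not match.** A withdrawer with a later event stays in the analysis until that event, while one without an event is removed at withdrawal. This pushes rates up.

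The rule governs the primary test, the key secondary VTE endpoint, the sensitivity analyses and the competing-risk analysis. Discontinuation was high enough to raise the planned enrolment from about 700 to about 800.

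**Working it through.** **Inputs from the SAP.** Section 1.4: "Primary efficacy composite endpoint event rate in the placebo arm: 14.5" and "Primary efficacy composite endpoint event rate in the rivaroxaban arm: 6" (per cent), "Probability of dropping out of the study: 20" (per cent), 350 per arm, two-sided 5%. Visit target days 56, 112 and 180 are from Section 2.1.

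**The plan's own figure.** Evaluable per arm: 350 × 0.8 = 280. With mean rate 0.1025, z = [0.085·√280 − 1.96·√(2·0.1025·0.8975)] / √(0.145·0.855 + 0.06·0.94) = (1.422 − 0.841)/0.425 = 1.37, so power is 91.5%. The stated >90% is reproduced and this point does not touch it. The implied HR is ln(0.94)/ln(0.855) = 0.395.

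**Treatment of a withdrawer**

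| | Event by Day 180 | No event |
|---|---|---|
| Followed to | the event, even after withdrawal | recorded withdrawal |
| Source | 2.5, 4.6(2a) | 2.6.1, 4.6(2b) |

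**Hand example, placebo.** Assume constant hazard, all events symptomatic, and 20% of those still at risk lost on Day 90.

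- Survival per half-period is √0.855 = 0.9247. At risk on Day 90: 350 × 0.9247 = 323.6; lost 64.7; remaining 258.9.
- Events from Day 90 to 180: 258.9 × 0.0753 = 19.5 among those remaining and 64.7 × 0.0753 = 4.9 among those lost.
- *Mismatched windows, withdrawal recorded on Day 90, all later events captured.* Risk set 258.9 + 4.9 = 263.8, events 24.4. Survival 0.9247 × 239.4/263.8 = 0.839, a rate of 16.1%.
- *Silent loss, withdrawal recorded only on Day 180, nothing captured.* Survival 0.9247 × (323.6 − 19.5)/323.6 = 0.869, a rate of 13.1%.
- *Both windows stopped at Day 90 for those lost.* Survival 0.9247 × 239.4/258.9 = 0.855, a rate of 14.5%.
- *Both windows extended to Day 180.* Survival 0.9247 × (323.6 − 24.4)/323.6 = 0.855, again 14.5%.

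The same steps at 6.0% give 6.7% (mismatch) and 5.4% (silent loss). The implied HR is 0.396 in both cases.

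**Simulation, true placebo rate 14.5%.** Assumptions not in the SAP: 35% of events found only by scan; withdrawal uniform over 180 days; part of it silent, with an exponential lag from last observation to recorded withdrawal; an exit scan for the rest. With no later capture, the SAP rule gives:

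| Withdrawal | Silent share | Mean lag | Day 180 rate | Error |
|---|---|---|---|---|
| 20% | half | 56 d | 14.2% | −0.3 |
| 20% | all | 90 d | 13.5% | −1.0 |
| 40% | half | 56 d | 13.9% | −0.6 |
| 40% | all | 90 d | 12.5% | −2.0 |

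Across the same four scenarios, by share of missed symptomatic events captured later:

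| Rule | Half captured | All captured |
|---|---|---|
| SAP as written | 13.5–15.0% | 14.5–16.0% |
| Earlier censoring only, event window left open | 14.9–15.8% | 15.4–16.9% |
| One observed window for both | 14.4–14.8% | 14.4–14.8% |

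A second model had exponential withdrawal of 20–40%, 20–40% of events asymptomatic, no exit scan and no recording lag. It gave 13.6–14.3% with no capture, 14.7–15.6% with half and 15.5–17.5% with full capture; the HR stayed at about 0.39–0.40.

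**Unequal loss.** With 25% of withdrawals silent in one arm and 75% in the other, and no capture, the HR moved 2–3% at 20% withdrawal and 5–8% at 40%. The direction depended on which arm lost more.

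**The case against.** The strongest reply is that the SAP already learns about these subjects. It asks for a scan when drug is stopped, contacts everyone at Day 210, and counts events after withdrawal. Section 5.2.5.2 turns withdrawers with unknown Day 210 status into events, and the Post-Randomization analysis (2.6.3) censors at last contact. Under equal loss the HR does not move. If sites record withdrawal as the date of last contact, the first fault shrinks or vanishes.

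Much of this stands. A reader might infer that the primary event rate is simply understated; the SAP does not support that, because counting events after withdrawal works the other way. A reader might also infer that two programmers would derive different datasets. Section 4.6(2b) fixes the date for withdrawers, so the difficulty is that the fixed date departs from the stated principle.

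The safeguards still leave the gap open:

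- The exit scan follows the last dose. A subject may stop drug, stay in the study and be lost later.
- A telephone call cannot find asymptomatic proximal DVT, a primary component.
- Section 5.2.5.2 covers only unknown Day 210 status and places its imputed events at the same withdrawal date. Withdrawers known to be event-free at Day 210 stay censored at withdrawal.
- The Post-Randomization analysis is supportive and does not change the primary rule.

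**Conclusion.** The defect is in the text: the censoring date need not be an assessment date, and withdrawers' events and censoring run on different windows. The Kaplan-Meier rates can be wrong in either direction. In the four main scenarios they are about 0.3–2.0 points too low with no later capture and up to about 1.5 points too high with full capture. The model without recording lag reaches 17.5 − 14.5 = 3.0 points too high, at 40% withdrawal.

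The primary comparison is little affected if loss and capture are equal between arms. Whether they are cannot be judged from the SAP. Silent share, lag, capture rate, scan-detected share and the actual withdrawal rate are all assumed, and withdrawal was taken as unrelated to VTE risk. This should be corrected, but it does not by itself undermine the primary test.

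**What to change.** For VTE endpoints, use one observed window per subject for both events and censoring.

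1. In 2.6.1 and 4.6(1b, 2b), delete the bracketed completion/withdrawal dates. Censor at the last date on which study outcomes were actually assessed, or at death if earlier. The double-blind end date serves only if such an assessment took place on it.
2. In 2.5 and 4.6(2a), count events in the primary analysis only up to that same date. An event reported between visits by a subject still in follow-up counts on its own date, as now.
3. As a stated alternative or sensitivity analysis, where the Day 210 contact establishes outcomes to Day 180, extend both windows to Day 180 for every withdrawer with known status, with or without an event. State that asymptomatic DVT is not ascertained over the added time.
4. Leave all-cause mortality on vital-status dates.

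Step 1 without step 2 should not be adopted: it widens the mismatch and overstated the rate in both capture columns above.

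The cost is SAP wording and one derivation from visit, scan and contact dates, before database lock. The primary analysis loses a little person-time and some post-withdrawal events, so intervals widen slightly.
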